3.3.3 Handling of Unscheduled Visits

See section [3.3.2](#).

3.3.4 Multiplicity/Multiple Comparisons

As this is an early phase safety study, no formal statistical hypothesis tests or multiplicity adjustment will be performed.

3.3.5 Handling of Protocol Deviations in Study Analysis

Deviations from protocol will be assessed as “important” (IPD) or “non-important”. The final classification will be made prior to clinical data lock and all IPDs will be identified and documented by the study team prior to unblinding of the trial. Further details are described in the protocol deviation plan. IPDs will include following categories:

- Inclusion criteria
- Exclusion criteria
- Discontinuation criteria for study product met but participant not withdrawn from study treatment
- Discontinuation criteria for overall study withdrawal met but participant not withdrawn from study
- Investigational product deviation
- Excluded medication taken
- Deviations related to study procedure
- Other important protocol deviations

Protocol deviations will not be a reason for exclusion from analyses.

4 STATISTICAL ANALYSIS

This section provides information on definitions, derivation and analysis/data presentation per domain.

4.1 Study Population

The domain study population covers subject disposition, analysis sets, protocol deviations, demographics, baseline characteristics, medical history, prior and concomitant medication and study drug compliance.

4.1.1 Subject Disposition and Completion Status

4.1.1.1 Definitions and Derivations

Disposition will be based on the Screened analysis set and following statuses are defined:

- Screened will be defined as a participant who signed ICF.
- Screen failure will be defined as a participant who signed ICF but are not subsequently randomised to a treatment group.
- Randomised will be defined as a participant who has been randomised to a treatment group.
- Randomised, not treated will be defined as a participant who has been randomised to a treatment group but who did not receive any dose of study intervention.
- Started treatment will be defined as a participant who has received at least one dose of study intervention.
- Completed treatment will be defined as a participant who has not permanently prematurely discontinued study intervention during the study.
- Discontinued treatment will be defined as a participant who have permanently prematurely discontinued study intervention.
- Completed planned treatment period will be defined as participant who has completed this period defined in section 3.3.1.2.
- Completed study will be defined as a participant who has completed all phases of the study including the follow-up visit.
- Withdraw from the study will be defined as a participant who did not complete the study.

4.1.1.2 Presentation

Subject disposition and completion status will be described by treatment group and for the total number of participants. Number of participants in each disposition status category will be presented, when applicable, percentages will also be presented. The reason for screen failed, discontinued treatment and withdrawn from study will also be presented based on reasons captured in CRF.

Listings for individual disposition statuses will be provided.

4.1.2 Analysis Sets

4.1.2.1 Definitions and Derivations

For definitions of the analysis sets see section [3.2](#).

4.1.2.2 Presentation

The number of participants included FAS and PKS, as well as the number of randomised participants excluded from them will be presented in a summary table overall and by treatment group.

Listing presenting subjects excluded from analyses sets will be provided.

4.1.3 Protocol Deviations

4.1.3.1 Definitions and Derivations

Only IPDs will be presented. The IPD categories to be presented are defined in section [3.3.5](#).

4.1.3.2 Presentation

The number and percentage of participants with at least one IPD category as well as the number and percentage of subjects, meeting each IPD category will be provided by treatment group and in total.

All the important protocol deviations will be listed by participant.

4.1.4 Demographics

4.1.4.1 Definitions and Derivations

Demographics variables include:

- Age (years)
- Age group (years) with categories: <30, >=30 - <50, >=50 - <65, >=65
- Sex with categories: Male, Female
- Race with categories: American Indian or Alaska Native, Asian, Black or African American, Native Hawaiian or Other Pacific Islander, White, Other, Multiple (if multiple races have been reported), Not reported.
- Ethnicity with categories: Hispanic or Latino, Not Hispanic or Latino, Not reported

4.1.4.2 Presentation

Demographics will be presented by treatment group and total. Age will be presented as a continuous variable with descriptive statistics and categorically by age group. Sex, race and

ethnicity will be presented as categorical variables. Demographics will also be presented for Japanese sub-population.

Per participant listing including demographics will be provided.

4.1.5 Baseline Characteristics

4.1.5.1 Definitions and Derivations

Baseline characteristics include:

- Height (cm)
- Body weight (kg)
- Body weight group (kg) with categories: <50, >=50 - <75, >=75 - <90, >=90 - <120, >=120
- BMI (kg/m²)
- BMI group (kg/m²) with categories: Underweight (<18.5), Normal weight (>=18.5 - <25), Overweight (>=25 - <30), Obese (>=30)

4.1.5.2 Presentation

Baseline patient characteristics will be presented descriptively by treatment group and overall. Baseline patient characteristics will also be presented for Japanese sub-population.

Per participant listing including certain baseline characteristics will be provided.

4.1.6 Disease Characteristics

4.1.6.1 Definitions and Derivations

The following disease characteristics for cirrhosis will be presented at baseline:

- MELD score (see section 3.3.1.6)
- Child-Pugh score (see section 3.3.1.6)
- Ascites with categories: Grade 1, Grade 2, Grade 3, Unknown, Diuretic resistant ascites
- Alcohol usage with categories: Current, Former, Never
- AUDIT score
- Nicotine usage with categories: Current, Former, Never

- eGFR (mL/min/1.73m²), based on eGFR1 (see section 3.3.1.6).
- eGFR group (mL/min/1.73m²), based on eGFR1 (see section 3.3.1.6) with categories: <60, >=60 - <90, >=90
- CCI [REDACTED]
- CCI [REDACTED]
- Systolic blood pressure (mmHg)
- Diastolic blood pressure (mmHg)
- Total body fat (kg)
- Total body water volume (L)
- Total extracellular water volume (L)
- Total intracellular water volume (L)
- Loop-diuretic usage with categories: Yes, No
- CCI [REDACTED]
- Type 2 diabetes with categories: Yes, No
- HbA1c (%)
- HbA1c for subjects with Type 2 diabetes (%)
- HbA1c for subjects without Type 2 diabetes (%)
- Non-selective beta blockers usage with categories: Yes, No
- Alcohol consumption (units)

The following cirrhosis etiology characteristics will be presented at baseline with categories Yes, No:

- Alcohol
- Hepatitis B

- Hepatitis C
- NASH
- Hemochromatosis
- Autoimmune hepatitis
- Wilson's Disease
- A1AD
- Sarcoid
- Unknown/idiopathic
- Other cause of cirrhosis

4.1.6.2 Presentation

Baseline disease characteristics will be presented descriptively by randomised treatment group and overall. Variables in section 4.1.6.1 not specified as categorical are continuous. The presentation will be descriptive and follow the rules defined in section 3.3. Baseline disease characteristics for certain characteristics will also be presented for Japanese sub-population.

A separate table of cirrhosis etiology will be presented descriptively by randomised treatment group and overall. This information will also be listed.

4.1.7 Medical History and Concomitant Disease

4.1.7.1 Definitions and Derivations

Medical and surgical history will be coded according to MedDRA and will be summarized by system organ class (SOC) and preferred term (PT).

4.1.7.2 Presentation

Medical and surgical history will be presented descriptively by treatment group and total. Percentages will be calculated with number of subjects in the analysis set as denominator. Subjects are only counted once per SOC and PT regardless of the number of occurrences within each category. PT will be presented within the relevant SOC and sorted by international order of SOC and alphabetically by PT.

4.1.8 Prior and Concomitant Medications

4.1.8.1 Definitions and Derivations

Prior medication is defined as any medication taken by the participant prior to the date of first dose of randomised treatment, regardless of when the medication ended. If medication is marked as taken prior to study start in the CRF the medication will be prior medication.

A medication will be concomitant if the medication end date is on or after the date of first dose of randomised treatment, or if the medication is ongoing at the study end.

Medications with completely missing end dates will be concomitant.

Disallowed concomitant medication are defined in Section 6.9.1, Prohibited Medications of the CSP. All other concomitant medications are classified as allowed.

Prior and concomitant medications will be reported by ATC classification and generic drug name (according to WHODrug).

4.1.8.2 Presentation

Prior, allowed concomitant and disallowed medications will be presented descriptively by treatment group and total. Percentages will be calculated with the number of subjects in the analysis set as denominator. Subjects are only counted once per ATC classification and generic drug name regardless of the number of medications within each category. Generic drug name will be presented nested within the relevant ATC classification and sorted alphabetically by ATC and then generic drug name.

Prior medications, disallowed concomitant medications, and allowed concomitant medications will be presented separately.

4.1.9 Study Drug Compliance

4.1.9.1 Definitions and Derivations

The percentage of treatment compliance for zibotentan/placebo for zibotentan will be calculated from the number of capsules returned as:

$$\frac{\text{Capsules dispensed} - \text{Capsules returned}}{\text{Capsules expected to be taken}} * 100$$

The percentage of treatment compliance for dapagliflozin/placebo for dapagliflozin will be calculated from the number of tablets returned as:

$$\frac{\text{Tablets dispensed} - \text{Tablets returned}}{\text{Tablets expected to be taken}} * 100$$

The overall percentage compliance will be calculated from the number of capsules and tablets returned as:

$$\frac{\text{Capsules and Tablets dispensed} - \text{Capsules and Tablets returned}}{\text{Capsules and Tablets expected to be taken}} * 100$$

The number of capsules and/or tablets expected to be taken is one capsule and one tablet per day starting at the date of first dose to the earliest date of end of treatment, lost to follow up or death, excluding days of dose interruption.

Percent of compliance will also be categorized into three groups, these are:

- <80%
- $\geq 80\%$ to $<120\%$.
- $\geq 120\%$

For all calculations of compliance, dispensed and returned refers to capsules/tablets taken at clinic and at home.

4.1.9.2 Presentation

Compliance will be presented by treatment group and total. Compliance will be presented for zibotentan/placebo for zibotentan, as well as for dapagliflozin/placebo for dapagliflozin and also overall. This will be done as a continuous variable with descriptive statistics and categorically by compliance group.

4.2 Endpoint Analyses

This section covers details related to the endpoint analyses such as key and exploratory endpoints including sensitivity analyses.

The estimand attributes Population, Treatment and Intercurrent event strategy are the same for all estimands and defined below. Attributes Endpoint and Population level summary are defined for each objective in [Table 7](#).

Population: Patients with cirrhosis with or without a history of decompensation, and who meet eligibility criteria as defined by the inclusion and exclusion criteria. See CSP for details.

Treatment: Fixed daily dose of zibotentan and dapagliflozin in combination, zibotentan monotherapy or placebo, in addition to their standard of care (SoC). See CSP for details.

Intercurrent event strategy: In general the treatment policy strategy will be used e.g. for premature treatment discontinuation due to any reason or prohibited medication.

Measurements for the variables of interest will be collected and analysed regardless of intercurrent events. For terminal events (i.e. death) a while-alive strategy will be applied.

Terminal events are expected to be few without substantial impact on the key and exploratory analyses.

Table 7 Key and Exploratory objectives

Statistical / Estimand category	Endpoint	Population/Analysis set	Intercurrent event strategy	Population level summary (analysis)	Details in section
Key objective 1: To evaluate the effect of zibotentan/dapagliflozin versus corresponding zibotentan monotherapy on a composite endpoint of fluid retention.					
Primary analysis	
Occurrence of any of the following components of this composite endpoint from baseline to Week 6:
 
 • > 2 kg increase from baseline in body weight (office-based) • > 2 L increase from baseline in total body water • Increase from baseline in 2 or more loop-diuretic equivalents (see section 3.3.1.5 for details) • Fluid retention AEs 	
Estimand population: See above for respective arms.
 
Analysis set: FAS
	Treatment policy strategy	Risk difference	4.2.1
Key objective 2: To evaluate the effect of zibotentan/dapagliflozin and zibotentan monotherapy versus placebo on a composite endpoint of fluid retention.					

Statistical / Estimand category	Endpoint	Population/Analysis set	Intercurrent event strategy	Population level summary (analysis)	Details in section
Primary analysis	
Occurrence of any of the following components of this composite endpoint from baseline to Week 6:
 
 • > 2 kg increase from baseline in body weight (office-based) • > 2 L increase from baseline in total body water • Increase from baseline in 2 or more loop-diuretic equivalents^a • Fluid retention AEs 	
Estimand population: See above for respective arms.
 
Analysis set: FAS
	Treatment policy strategy	Risk difference	4.2.1
Key objective 3: To evaluate the effect of zibotentan/dapagliflozin versus corresponding zibotentan monotherapy on body weight, body water volumes, and body fat mass.					
Primary analysis	
Change in body weight (kg) over time course of study (home-based monitoring).
 
Change from baseline in body weight, total body water, extracellular and intracellular water volumes, body fat mass at Week 6 (office-based monitoring).
	
Estimand population: See above for respective arms.
 
Analysis set: FAS
	Treatment policy strategy	Least square mean difference in change from baseline	4.2.2
Key objective 4: To evaluate the effect of zibotentan/dapagliflozin and zibotentan monotherapy versus placebo on body weight, body water volumes, and body fat mass.					

Statistical / Estimand category	Endpoint	Population/Analysis set	Intercurrent event strategy	Population level summary (analysis)	Details in section
Primary analysis	
Change in body weight (kg) over time course of study (home-based monitoring).
 
Change from baseline in body weight, total body water, extracellular and intracellular water volumes, body fat mass at Week 6 (office-based monitoring).
	
Estimand population: See above for respective arms.
 
Analysis set: FAS
	Treatment policy strategy	Least square mean difference in change from baseline	4.2.2
Key objective 5: To evaluate the effect of zibotentan/dapagliflozin versus corresponding zibotentan monotherapy on total loop-diuretic equivalents use. ^a					
Primary analysis	Change in total dosage of loop-diuretic equivalents use from baseline to Week 6 ^a .	
Estimand population: See above for respective arms.
 
Analysis set: FAS
	Treatment policy strategy	Least square mean difference in change from baseline	4.2.3
Key objective 6: To evaluate the effect of zibotentan/dapagliflozin and zibotentan monotherapy versus placebo on total loop-diuretic equivalents use. ^a					
Primary analysis	Change in total dosage of loop-diuretic equivalents use from baseline to Week 6 ^a .	
Estimand population: See above for respective arms.
 
Analysis set: FAS.
	Treatment policy strategy	Least square mean difference in change from baseline	4.2.3
Key objective 7: To evaluate the effects of zibotentan/dapagliflozin versus corresponding zibotentan monotherapy on the composite of total body water and total dosage of loop-diuretic equivalents. ^a					
Primary analysis	
Occurrence of either of the two components of this composite:
 
 ● > 3 L increase from baseline in total body water volume 	
Estimand population: See above for respective arms.
 
Analysis set: FAS
	Treatment policy strategy	Risk difference	4.2.4

Statistical / Estimand category	Endpoint	Population/Analysis set	Intercurrent event strategy	Population level summary (analysis)	Details in section
	from baseline to Week 6. 
 • Increase from baseline in 3 or more loop-diuretics equivalents use from baseline to Week 6 ^a. 				
Key objective 8: To evaluate the effects of zibotentan/dapagliflozin and zibotentan monotherapy versus placebo on the composite of total body water and total dosage of loop-diuretic equivalents. ^a					
Primary analysis	Occurrence of either of the two components of this composite: 
 • > 3 L increase from baseline in total body water volume from baseline to Week 6. • Increase from baseline in 3 or more loop-diuretics equivalents use from baseline to Week 6 ^a. 	Estimand population: See above for respective arms. Analysis set: FAS	Treatment policy strategy	Risk difference	4.2.4
Key objective 9: To evaluate the effect of zibotentan/dapagliflozin versus corresponding zibotentan monotherapy on office-based systolic and diastolic blood pressure.					
Primary analysis	Absolute change in systolic and diastolic blood pressure from baseline to Week 6.	Estimand population: See above for respective arms. Analysis set: FAS	Treatment policy strategy	Least square mean difference in change from baseline	4.2.5
Key objective 10: To evaluate the effect of zibotentan/dapagliflozin and zibotentan monotherapy versus placebo on office-based systolic and diastolic blood pressure.					

Statistical / Estimand category	Endpoint	Population/Analysis set	Intercurrent event strategy	Population level summary (analysis)	Details in section
Primary analysis	Absolute change in systolic and diastolic blood pressure from baseline to Week 6.	Estimand population: See above for respective arms. Analysis set: FAS	Treatment policy strategy	Least square mean difference in change from baseline	4.2.5
Exploratory objective 1: To characterise the plasma exposure to zibotentan and dapagliflozin.					
Primary analysis	Plasma concentrations of zibotentan and dapagliflozin.	Estimand population: See above for respective arms. Analysis set: PKS	Treatment policy strategy	Descriptive statistics	4.2.6
Exploratory objective 2: To evaluate the effect of zibotentan/dapagliflozin in combination and zibotentan monotherapy versus placebo on CCI and/or CCI .					
Primary analysis	Percentage and absolute change in CCI and CCI from baseline to Week 6.	Estimand population: See above for respective arms. Analysis set: FAS	Treatment policy strategy	Mean difference between treatment groups	4.2.7
Exploratory objective 3: To evaluate the effect of zibotentan/dapagliflozin and zibotentan monotherapy versus placebo on liver health and portal hypertension biomarkers.					
Primary analysis	
 Percentage and absolute change in AST and ALT from baseline to Week 6. Absolute change in MELD score from baseline to Week 6. 	Estimand population: See above for respective arms. Analysis set: FAS	Treatment policy strategy	Mean difference between treatment groups	4.2.8
Exploratory objective 4: To assess the effect of zibotentan/dapagliflozin in combination and zibotentan monotherapy versus placebo on plasma/serum levels of CCI .					
Primary analysis	Changes in blood and urine biomarkers across time from baseline to Week 6.	Estimand population: See above for respective arms. Analysis set: FAS	Treatment policy strategy	Mean difference between treatment groups	4.2.9

Statistical / Estimand category	Endpoint	Population/Analysis set	Intercurrent event strategy	Population level summary (analysis)	Details in section
Exploratory objective 5: To evaluate the effect of zibotentan/dapagliflozin versus zibotentan monotherapy and placebo on eGFR.					
Primary analysis	Change in eGFR from baseline to Week 6.	Estimand population: See above for respective arms. Analysis set: FAS	Treatment policy strategy	Mean difference between treatment groups	4.2.10
Exploratory objective 6: To evaluate the effect of zibotentan/dapagliflozin and zibotentan monotherapy versus placebo on fatigue, abdominal symptoms, physical functioning and health-related quality of life					
Primary analysis	Change from baseline to Week 6 in CLDQ Fatigue and Abdominal Symptoms scores, SF-36v2 Physical Functioning score, Total CLDQ score, SF-36v2 Physical Component Summary score, SF-36v2 Mental Component Summary score, Patient Global Impression of Severity - Liver Disease	Estimand population: See above for respective arms. Analysis set: FAS	Treatment policy strategy	Descriptive statistics	4.2.11
Exploratory objective 7: To collect and store plasma, serum and urine samples for exploratory research aimed at exploring biomarkers involved in PK, PD, safety and tolerability related to zibotentan and dapagliflozin in combination versus placebo or CC1					
This objective will not be reported in the CSR.					
-	Evaluation of changes in blood and urine biomarkers	-	-	-	-

a See section [3.3.1.5](#) for details.

For timing of data collection for above endpoints please see SoA in CSP.

Unless otherwise stated the analyses within each section below will be applied for the treatment groups as indicated in the objectives. In general for comparisons of key objectives the following comparisons will be made: zibotentan/dapagliflozin versus zibotentan monotherapy, zibotentan/dapagliflozin versus placebo and zibotentan monotherapy versus placebo.

In case of convergence issues for the analysis model the **CCI** [REDACTED], defined as **CCI** [REDACTED], will be adjusted appropriately to accommodate convergence for the model.

Assessed values of the form ‘<x’ (below the lower limit of quantification) will be imputed as ‘x’ in calculations for key and exploratory objectives.

Subgroup analyses defined in sections below will be done if adequate numbers of observations are available.

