- Results need to be available before the randomisation visit (Visit 2).
- Study intervention intake will take place at the study centre and at home when not visiting the study centre.
- CCⁱ to be assessed ≥ 3 hours after study intervention administration at Visit 6. A CCⁱ assessment of CCⁱ s and/or CCⁱ should only be done if CCⁱ to complete an accurate CCⁱ and/or CCⁱ measurement. CCⁱ should only be done if CCⁱ is available.
- CCⁱ must not take place earlier than at least 3 hours after a light meal, such as breakfast. If the participant is on a non-selective beta-blocker, the morning dose should not be taken, but taken directly after the CCⁱ.
- If a SAE occurs within 48 hours after the last dose, a PK sample will be taken if possible. The exact time of last dosing and of blood sampling will be recorded.
- Pre-dose sample in all participants (both Japanese and non-Japanese).
- Pre-dose sample and dosing at the study centre at every visit. Pharmacokinetics sample to be done at early termination visit as well. If no dosing takes place, sample at any time during the study centre visit and document exact date and time.

- k. Pharmacokinetics profile only for Japanese patients. Samples for PK profile collected over 5 hours at the study centre. Sampling times: pre-dose, 0.5 to 1.0, 1.5 to 2.0, 2.5 to 3.0, 3.5 to 4.0, 4.5 to 5.5 hours post-dose; exact clock times need to be documented. See Section [5.3.1](#) for further details on meal restrictions.
- l. Pharmacokinetics profile can be done at Visit 4 if not possible at Visit 5. At the day selected for the PK profile, the study intervention must be administered at the study centre so that PK sampling according to schedule is possible.
- m. A post-dose sample is taken as late as possible after dosing on the dose day (at least 1h after dosing); the exact actual sampling time needs to be recorded.
- n. Visit 6 is planned End of Treatment (EoT) visit. If participant terminates early from the study (ie Withdraw consent), please perform examinations as Visit 6.
- o. Baseline PRO Questionnaires to be completed before treatment initiation.

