6.5 Study Intervention Compliance

At the visits specified in the SoA ([Table 1](#)), participants will receive study intervention at the study centre or will take the study intervention at home. When participants are dosed at the site, they will receive study interventions directly from the investigator or designee, under medical supervision. The date and time of the dose administered on the visit day, as well as the date and time of the dose taken the day before each visit to the study centre, will be recorded in the source documents and recorded in the eCRF. The dose of study intervention and study participant identification will be confirmed at the time of dosing by a member of the study centre staff other than the person administering the study intervention.

A record of the number of study interventions (capsules and tablets) dispensed to and administered by each participant must be maintained and reconciled with study intervention

and compliance records. Intervention start and stop dates, including dates for intervention delays will also be recorded in the eCRF.

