7.1 Discontinuation of Study Intervention

It may be necessary for a participant to permanently discontinue (definitive discontinuation)

study intervention.

An individual participant may be discontinued from study intervention in the following situations:

- CCI [REDACTED]; Section CCI [REDACTED].
- New diagnosis of CCI [REDACTED] of the CCI [REDACTED].
- New or worsening of symptoms of CCI [REDACTED] other than CCI [REDACTED] that is not responsive to CCI [REDACTED] doses of CCI [REDACTED].
- Overt encephalopathy (Grade 2 or higher), variceal haemorrhage, or hepatocellular cancer.
- Serious/severe CCI [REDACTED].
- Serious/severe CCI [REDACTED].
- Diabetic ketoacidosis including euglycaemic DKA have been reported with use of dapagliflozin. Consider temporary interruption of study intervention if DKA is suspected. The participant should be promptly evaluated. If DKA is confirmed, study intervention should be discontinued permanently (see Section 7.1.1 for details). If DKA is not confirmed, re-start of study intervention should be considered.
- When DILI is suspected and re-start of the study intervention is not permitted based on the algorithm outlined in Section 7.1.2.
- eGFR < 45 mL/min/1.73 m² confirmed upon repeat testing.
- Development of CCI [REDACTED] or other causes of CCI [REDACTED].
- Liver transplantation.
- Transjugular intrahepatic portosystemic shunt.
- Participant decision. The participant is at any time free to discontinue treatment, without prejudice to further treatment.
- An AE that, in the opinion of the investigator or AstraZeneca, warrants discontinuation from further dosing.
- Severe non-compliance with the CSP.
- Pregnancy: if a female participant or the female partner of a male participant becomes pregnant during the course of the study, study intervention should be discontinued immediately, and an AstraZeneca representative notified.
- Safety reasons as judged by the investigator and/or sponsor where continued treatment may put participant at undue risk.

Note that discontinuation from study intervention is NOT the same thing as a withdrawal from

the study (Section 7.2).

Participants who prematurely discontinue study intervention should remain in the study and attend all planned study visits including the Follow-up Visit as per SoA (Table 1).

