4.2.6.4 Primary Analysis of exploratory objective

The data will be descriptively summarised by treatment group, visit, and time-point. Geometric mean and CV will be presented in addition to arithmetic mean and SD. PK assessments that should only be collected once according to schedule of activities in CSP will be summarised using the assessment closest to target date even if outside of visit windowing.

Additional PK analyses may be conducted as appropriate but will be reported outside the CSR.

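### Treatment policy applied to plasma concentrations lets off-drug samples into the pre-dose PK summaries and can bias reported on-drug exposure downward

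*SAP*

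**What the plan says.** SAP 4.2 states that "The estimand attributes Population, Treatment and Intercurrent event strategy are the same for all estimands and defined below". The strategy is treatment policy for premature discontinuation and prohibited medication: "Measurements for the variables of interest will be collected and analysed regardless of intercurrent events". Table 7 repeats treatment policy in the row for exploratory objective 1, whose aim is "To characterise the plasma exposure to zibotentan and dapagliflozin". The analysis set in that row is the PKS and the summary is descriptive. SAP 4.2.6.4 adds: "The data will be descriptively summarised by treatment group, visit, and time-point". The statistics include geometric mean and CV as well as arithmetic mean and SD.

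The protocol states treatment policy under key endpoints (9.4.2). Its PK section (9.4.4.1) names no strategy, so the extension to concentrations is made in the SAP.

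On data collection, Protocol 7.1 says: "Participants who prematurely discontinue study intervention should remain in the study and attend all planned study visits". The Schedule of Activities (Protocol 1.3) places the pre-dose PK sample at Visits 3, 4 and 5. The footnote to that row says: "If no dosing takes place, sample at any time during the study centre visit and document exact date and time". It also asks for a PK sample at early termination. Protocol 6.5 has the visit-day dose time captured and adds that "the date and time of the dose taken the day before each visit to the study centre, will be recorded" in the source documents and the eCRF.

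**The concern.** Treatment policy suits the fluid-retention and safety endpoints, where the effect of being assigned a regimen is of interest whether or not it is taken. A drug concentration is different. Exposure to the assigned dose has meaning only while the dose is being taken. A value obtained after stopping reflects when the participant stopped, not the exposure that the dose produces.

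These summaries are the exposure result planned for the CSR, because SAP 4.2.6.4 sends any additional PK analysis outside it. If off-drug samples are mixed in, the reported pre-dose mean partly describes interruption and discontinuation. A reader who informally compares the two zibotentan arms could then take a difference in discontinuation for a difference in exposure, although no such contrast is planned.

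**Working it through.** **Step 1. Can off-drug samples arise at Visits 3 to 5?** Yes, by design. Participants who discontinue stay on the visit schedule (Protocol 7.1). Temporary interruption is foreseen (Protocol 7.1). An undosed participant is still sampled (footnote to the pre-dose row, Protocol 1.3), and the pre-dose row is the only scheduled row that sample belongs to.

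**Step 2. Does any rule remove or label them?**

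- PKS definition (SAP 3.2): works at participant level; one detectable concentration of either drug is enough. The only sample-level exclusion is optional and covers samples after Visit 5.
- Visit windows (SAP 3.3.2): early-termination and unscheduled visits are mapped to a scheduled visit. If several values fall in one window, the one nearest the target day is used. That does not help when the only value at a visit is off drug.
- Protocol deviations (SAP 3.3.5): not grounds for exclusion.
- Values below the quantification limit (SAP 4.2): set to the limit, so an off-drug sample stays in the geometric mean as a low positive value.
- PK summary (SAP 4.2.6.4): no condition on last dose or actual sampling time.

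No rule removes them. By contrast, SAP 4.1.9.1 does leave interruption days out of the compliance denominator.

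**Step 3. How large could the effect be?** There is no plan figure to reproduce: the documents give no concentration, half-life, quantification limit or expected number of off-drug samples.

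Inputs: n = 22 samples per cell (planned participants per arm, Protocol 4.1); k off-drug samples, each at r times the typical trough. Both k and r are assumptions. The remaining samples are taken to share a common mean.

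- Geometric mean ratio, reported over true: r^(k/n)
- Arithmetic mean ratio: 1 − (k/n)(1 − r)

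Example, k = 1 and r = 0.1: geometric 0.1^(1/22) = 0.901; arithmetic 1 − (1/22)(0.9) = 0.959.

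| k | r | Geometric ratio | Arithmetic ratio |
|---|---|---|---|
| 0 | any | 1 | 1 |
| 1 | 0.5 | 0.969 | 0.977 |
| 1 | 0.1 | 0.901 | 0.959 |
| 1 | 0.01 | 0.811 | 0.955 |
| 2 | 0.5 | 0.939 | 0.955 |
| 2 | 0.1 | 0.811 | 0.918 |
| 2 | 0.01 | 0.658 | 0.910 |

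The geometric mean is the more sensitive of the two. A cell with fewer than 22 samples would move more for the same k.

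**The case against.** The strongest defence is that little depends on this result. The objective is exploratory and descriptive, and the study has no hypothesis tests. The number of off-drug samples by Visit 5 may be zero. The arithmetic mean moves much less than the geometric mean, and the median, reported by default under SAP 3.3, would barely move with one or two such samples among 22. Disposition, duration of exposure and compliance by arm would reveal an imbalance in stopping. Dose and sampling times are recorded, so the problem can be repaired later. An early-termination sample is not necessarily off drug, because Protocol 7.2 has drug stopped at withdrawal, and samples after Visit 5 may be left out of the PKS. All of this stands. It limits the size and priority of the point but does not supply the missing rule.

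It can also be argued that nothing labels an undosed sample as pre-dose. But the instruction to take it hangs on the pre-dose row, and the SAP offers no other time-point for it.

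Three stronger readings are tempting, and the documents do not support them:

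- A reader might infer that post-dose samples are averaged with troughs. Summaries are by time-point, and the post-dose sample and the Japanese profile have their own rows in the Schedule of Activities.
- A reader might infer that samples taken after a home dose on the visit morning are routinely mixed in. Protocol 1.1 and 4.1 place the visit-day dose at the study centre, so that would be off-protocol.
- A reader might infer that the dose choice is undermined. Protocol 4.3 rests on oncology safety data and an earlier hepatic and renal impairment study, not on this trial's PK summary.

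**Conclusion.** The point holds as a matter of what the SAP states, not merely of what it omits: treatment policy is assigned explicitly to plasma concentrations, and no sample-level rule counteracts it. Any off-drug sample at Visits 3 to 5 can bias the reported on-drug pre-dose mean downward. Under the assumed values, one such sample in 22 lowers the geometric mean by about 3% to 19% and two by about 6% to 34%; the arithmetic mean falls by about 2% to 5% and 5% to 9%. These ranges rest wholly on the assumed k and r.

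A reader might go further and conclude that the reported exposure will be wrong. The documents do not show that, because they give neither the number of off-drug samples nor their concentrations. The priority is low, but the rule as written does not answer the stated exposure question.

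**What to change.** In SAP Table 7, change exploratory objective 1 to a while-on-treatment strategy. In SAP 4.2.6.4, add a sample-level condition:

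- Pre-dose summary: only samples with a recorded dose on the previous day, drawn before any visit-day dose, and within a pre-specified interval since the last dose, chosen by the sponsor's pharmacokineticist.
- Post-dose summary: only samples with a recorded dose that day.
- All other samples (off drug, undosed and drawn at an unrestricted time, or early termination not meeting the condition): listed with time since last dose and left out of the means.
- The rule that takes the assessment nearest the target day, even outside its window: subject to the same condition.

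The cost is SAP wording and a programming filter. The dose times are already captured under Protocol 6.5, and the sampling time for undosed visits under the Schedule of Activities footnote. The downside is slightly fewer samples in some cells; no data are lost, because excluded samples remain in the listings.
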